3.2 Key Definitions

The following definitions will be used:

- **Baseline:** The baseline value is defined as the last available valid (quantifiable continuous or categorical value), non-missing observation for each subject prior to first study drug administration. Repeat and unscheduled assessments will be included in the derivation of the baseline values.
- **Change from Baseline:** The change from baseline value is defined as the difference between the result collected/derived at a post-baseline visit/time point and the baseline value.

The change from baseline value at each post-baseline visit/time point will be calculated for all continuous parameters using the following formula:

$$\text{Change from Baseline Value} = \text{Result at Visit/Time Point} - \text{Baseline Value}$$

The change from baseline value will only be calculated if the specific post-baseline visit/time point result and the baseline value for the parameter are both available and will be treated as missing otherwise.

- **Study day:** The study day of an event is defined as the relative day of the event starting with the date of the first study drug administration (reference date) as Day 1 (there will be no Day 0).

The study day of events occurring before the first study drug administration will be calculated as:

$$\text{Study Day} = (\text{Date of Event} - \text{Date of First Study Drug Administration})$$

For events occurring on or after Day 1, study day will be calculated as:

$$\text{Study Day} = (\text{Date of Event} - \text{Date of First Study Drug Administration}) + 1$$

Study days will only be calculated for events with complete dates and will be undefined for events that are 'Ongoing' at the end of the study.

Relative days compared to an alternative reference point will be calculated similarly, but the alternative starting reference start date will be used instead of the date of the first study drug dosing.

- **HBsAg loss:** quantitative HBsAg < 0.05 IU/mL at two or more consecutive measurements.
- **Sustained HBsAg loss:** quantitative HBsAg < 0.05 IU/mL at all visits (scheduled and unscheduled) for ≥ 6 months.

- HBsAg Seroconversion: HBsAg loss plus anti-HBs positivity at two or more consecutive measurements
- HBeAg loss (HBeAg+ subjects only): quantitative HBeAg < 0.14 IU/mL at two or more consecutive measurements
- HBeAg Seroconversion (HBeAg+ subjects only): HBeAg loss plus anti-HBe positivity at two or more consecutive measurements

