### 1.3. VIR-2218-1005 study

The cohort dosing strategy of this study is based on data collected from the VIR-2218-1001 regional study (Appendix 4). There are 2 planned cohorts (50 mg dose-level and 100 mg dose-level) for both Part One and Part Two of the study. For each of the planned 50 and 100 mg dose-level cohorts, 5 subjects will be randomized 4:1 to VIR-2218 or placebo administered 4 weeks apart on Day 1 and Week 4.

One optional cohort may be added to each study part (Part One and Part Two), wherein 5 subjects will be randomized 4:1 to VIR-2218 or placebo administered 4 weeks apart on Day 1 and Week 4 at a dose-level of up to 200 mg.

The optional cohorts may be initiated after SRC review of a minimum of 6 weeks of available safety and antiviral activity data from the 200 mg cohorts of the VIR-2218-1001 regional study.

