### 3.2. Secondary Endpoints

- PK parameters of VIR-2218 and possible metabolites (may include, but not limited to, maximum plasma concentration, time to reach maximum concentration, area under the concentration versus time curve [to last measurable timepoint and to infinity], percent of area extrapolated, apparent terminal elimination half-life, clearance, and volume of distribution)
- Maximum reduction of serum HBsAg from Day 1 until 12 weeks post last dose
- Number of subjects with serum HBsAg loss at any timepoint
- Number of subjects with sustained serum HBsAg loss for greater than or equal to 6 months post last dose
- Number of subjects with anti-HBs seroconversion at any timepoint
- For HBeAg-positive subjects (Part Two only): number of subjects with HBeAg loss and/or anti-HBe seroconversion at any timepoint

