### **Extended follow-up period:**

Subjects who require additional HBsAg monitoring will return to the clinical investigational site for in-person assessments. Extended follow-up visits will occur every 4 weeks starting at Week 20, and subjects will be followed until the HBsAg level returns to > 90% of the Day 1 predose level or Week 48, whichever comes earlier. Additional HBsAg monitoring may be discontinued at the Sponsor's discretion based on emerging data.

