2.3.2 Secondary endpoints

- PK parameters of VIR-2218 and possible metabolites (may include, but not limited to, maximum plasma concentration, time to reach maximum concentration, area under the concentration versus time curve [to last measurable timepoint and to infinity], percent of area extrapolated, apparent terminal elimination half-life, clearance, and volume of distribution).
- Maximum reduction of serum HBsAg from Day 1 until 12 weeks post last dose.
- Number of subjects with serum HBsAg loss at any timepoint.
- Number of subjects with sustained serum HBsAg loss for greater than or equal to 6 months.
- Number of subjects with anti-HBs seroconversion at any timepoint.
- For HBeAg-positive subjects (Part Two only): number of subjects with HBeAg loss and/or anti-HBe seroconversion at any timepoint.

CCI [REDACTED]

[REDACTED]

[REDACTED]

[REDACTED]

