13.1 Definition of variables

- Maximum reduction of serum HBsAg from Day 1 until Week 16.
 - Serum \log_{10} HBsAg levels by timepoint
 - Serum \log_{10} HBsAg Nadir level per subject
- Number of subjects with serum HBsAg loss.
- Number of subjects with sustained serum HBsAg loss for ≥ 6 months.
- Number of subjects with anti-HBs seroconversion.
- For HBeAg-positive subjects (Part Two only): number of subjects with HBeAg loss and/or anti-HBe seroconversion.

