15. CHANGES TO THE PLANNED ANALYSIS

Not applicable.

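### The SAP drops the last-dose anchor from the sustained HBsAg loss endpoint without declaring a change (minor)

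*SAP*

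**What the plan says.** The protocol gives the endpoint in the synopsis and again in Section 3.2, with the same words: "Number of subjects with sustained serum HBsAg loss for greater than or equal to 6 months post last dose".

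The SAP states it three times, each time without the reference to the last dose:

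- Section 2.3.2, endpoint list: "Number of subjects with sustained serum HBsAg loss for greater than or equal to 6 months".
- Section 3.2, definition: quantitative HBsAg below 0.05 IU/mL "at all visits (scheduled and unscheduled) for ≥ 6 months".
- Section 13.1, analysis variables: "Number of subjects with sustained serum HBsAg loss for ≥ 6 months".

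SAP Section 15, headed "CHANGES TO THE PLANNED ANALYSIS", reads "Not applicable". The SAP names protocol Amendment 2 as its source (Section 18).

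The omission is specific to this endpoint. In the same SAP 2.3.2 list, the maximum HBsAg reduction keeps its limit of 12 weeks after the last dose, and SAP 13.1 turns that limit into Week 16.

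**The concern.** The protocol endpoint concerns loss in relation to the end of VIR-2218 dosing. The SAP definition is an unbroken six-month run that may start at any time. These are different quantities, so one subject could be a success under one document and not under the other.

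A programmer working from SAP 3.2 would apply the unanchored rule and see no deviation to report, because Section 15 records none. The count in the study report would then carry the name of the protocol endpoint without following its wording. Each full cohort has four active subjects, so one reclassified subject moves that cohort's percentage by 1/4 = 25 points.

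**Working it through.** There is no sample-size or power figure to reproduce. The check applies each rule to the visit schedule.

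**Inputs**

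- Doses are "administered 4 weeks apart on Day 1 and Week 4" (protocol 1.3). Appendix 2 puts the last dose at Day 29. Both doses are assumed given.
- Nominal HBsAg visits (Appendix 2): Weeks 1 to 8 weekly (Days 8 to 57), Week 12 (Day 85) and Week 16 (Day 113). After that, "Extended follow-up visits will occur every 4 weeks starting at Week 20" (Day 141), up to Week 48 (Day 337).
- Entry HBsAg is above 150 IU/mL (protocol 5.2). Loss is below 0.05 IU/mL (SAP 3.2).
- Neither document gives six months in days. I assume 183 and test 180 to 184.
- Run length is taken from the first to the last negative visit.

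**Two readings of the protocol phrase**

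- *Duration reading*: at least six months of loss, counted only from the last dose.
- *Status reading*: confirmed loss still present at a visit at least six months after the last dose.

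**Key dates**

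- Six months after the last dose: 29 + 183 = Day 212.
- Week 28 is Day 197, and 197 − 29 = 168 days after the last dose. Week 32 is Day 225, and 225 − 29 = 196 days after it. Week 32 is therefore the first scheduled visit past six months.
- Latest first-negative visit that can meet the SAP rule: Week 20 (337 − 141 = 196 days). Week 24 is too late (337 − 169 = 168 days).

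**Example patterns**

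| Loss from–to | Run length | Days from last dose to end of run | SAP | Duration reading | Status reading |
|---|---|---|---|---|---|
| Week 1–28 | 197 − 8 = 189 | 168 | yes | no | no |
| Week 2–28 | 197 − 15 = 182 | 168 | yes only if six months ≤ 182 days | no | no |
| Week 24–48 | 337 − 169 = 168 | 337 − 29 = 308 | no | no | yes |

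**All patterns.** The 18 visits from Week 1 to Week 48 give 18 × 17 / 2 = 153 unbroken runs of two or more visits.

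- At 183 days, 44 runs qualify under the SAP, 43 under the duration reading and 75 under the status reading.
- SAP against the duration reading: 1 run disagrees at 183 or 184 days, and 2 at 180 or 182 days. In every case the SAP says yes and the protocol no.
- SAP against the status reading at 183 days: 33 runs disagree. In 32 the SAP says no and the protocol yes; in 1 it is the reverse.

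These are counts of possible visit patterns, not probabilities.

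**How extreme the early case is.** log10(150 / 0.05) = log10(3000) ≈ 3.48. Loss at Week 1 or 2 needs a fall of more than that, in every eligible subject, after a single dose.

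**The case against.** The strongest defence is that the protocol phrase reads naturally as a duration counted after the last dose. On that reading the SAP differs only for loss that begins by Week 1 or 2 and ends between Weeks 28 and 32, which is close to hypothetical. The analysis is descriptive, with no hypothesis test (SAP 3.3). All antiviral data are listed by subject and HBsAg plots are planned (SAP 13.2), so either count can be rebuilt. This stands, and it is why the point is minor. It does not remove the textual mismatch or the silence of Section 15.

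A reader might infer more, in three ways that the documents do not support:

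- *That the SAP wrongly rejects late-onset loss.* The Week 24 to 48 pattern is a conflict only under the status reading. Under the duration reading it fails both rules. The protocol does not say which reading applies.
- *That Week 2 to 28 plainly meets the SAP rule.* It lasts exactly 182 nominal days and fails if six months is 183. With windows of ±2 days at Week 2 and ±7 at Week 28 it can span 173 to 191 days. Week 24 to 48 (±7 at each end) can span 154 to 182. The SAP excludes no out-of-window assessment (Section 3.1).
- *That an off-treatment cure claim is at stake.* Subjects stay on NrtI therapy, and the protocol mentions functional cure only as a potential, without tying it to this endpoint.

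**Conclusion.** The omission is real. It occurs in all three SAP statements of the endpoint and is not declared. As written, the SAP can count time before the Week 4 dose, and at least one nominal visit pattern (Week 1 to 28) is classified differently under either protocol reading and at every six-month length tested.

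Its practical size depends on the undefined protocol phrase. It is an edge case under the duration reading. It is broader under the status reading, where the SAP mainly leaves out later losses. Few events are expected given the fall required, and no error rate or power is affected. The 25-point shift arises only if a discordant event actually occurs in a cohort.

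The conclusion rests on nominal visit days, both doses given, and 180 to 184 days for six months. Severity: minor.

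**What to change.** Restore the protocol's last-dose anchor in SAP 2.3.2, 3.2 and 13.1, so that no time before the last dose counts. In SAP 3.2, state which reading of the phrase is used and how many days make six months.

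If the unanchored six-month run is also wanted, report it as a separate, labelled row and declare it in Section 15.

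Avoid writing a fresh rule that requires loss to be present at the first visit at least 26 weeks after the last dose and at every later visit. That would be a third definition. It would reject loss from Week 8 to Week 44 with rebound at Week 48 (309 − 57 = 252 days, all after the last dose), which meets the SAP rule and both protocol readings. It would accept loss from Week 28 to Week 48, which lasts only 337 − 197 = 140 days.

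The cost is SAP wording, settled before database lock and unblinding. The existing visits to Week 48 supply the data, so nothing new has to be collected.

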### 5. SUBJECT POPULATION

### 5.1. Number of Subjects and Subject Selection

A total of up to 30 adult subjects with chronic HBV infection without cirrhosis on NrtI therapy are planned to complete this study.

- **Part One Planned/Optional Dose Cohorts:** Up to 15 adult subjects with chronic HBV infection without cirrhosis who are HBeAg-negative on NrtI therapy
- **Part Two Planned/Optional Dose Cohorts:** Up to 15 adult subjects with chronic HBV infection without cirrhosis who are HBeAg-positive on NrtI therapy

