Blood sample for HBsAg	X	X	X	X	X	X	X	X	X	X	X	X	X	X	X	X
Blood sample for anti-HBs	X										X		X		X	Xs
Blood sample for HBeAg qualitative	X															
Blood sample for HBeAg quantitative for Part Two only t		X					X				X	X	X		X	Xs
Blood sample for anti-HBe for Part Two only	X										X		X		X	Xs
Blood sample for HBV DNA quantitation u	X	X					X				X	X	X	X	X	Xs

Study Stage	Screening		Dosing Period					Post-dose Follow-up Period b				b	Extended Follow-up Period °			
Study Visit Week				W1	W2	W3	W4ª	W5	W6	W7	W8	W12	W16/ET	W20	W24	
Study Visit Day	D-28 to -1	D1ª	D2	D8	D15	D22	D29a	D36	D43	D50	D57	D85	D113	D141	D169	Q28D
±Visit Window				±2	±2	±2	±2	±2	±2	±2	±2	±7	±7/ET	±7	±7	±7

Review/record AEs x	X	
Concomitant Medications	X	
NrtI medication adherence	X	

AE = adverse event; ECG = electrocardiogram; ET = early termination; CCI surface antigen; HBV = Hepatitis B Virus; NrtI = nucleoside/nucleotide; PK = pharmacokinetics

HBeAg = hepatitis e-antigen; HBsAg = hepatitis B

Note: When scheduled at the same timepoints, the assessments of vital signs and 12-lead ECGs must be performed before blood sample collections.

- a Assessments performed predose unless otherwise specified.
- b If a subject withdraws prematurely from the study prior to their Week 16 visit, ET assessments should be performed.
- Additional HBsAg monitoring is required for subjects with  $a \ge 1 \log_{10}$  change from baseline (Day 1 predose level) decrease in HBsAg achieved by the Week 16 visit. Extended follow-up visits will occur every 4 weeks starting at Week 20, and subjects will be followed until the HBsAg level returns to > 90% of the Day 1 predose level or Week 48, whichever comes earlier. Additional HBsAg monitoring may be discontinued at the Sponsor's discretion based on emerging data.
- d A complete medical history will be taken at screening including HBV genotype if available. Any changes should be updated prior to dosing.
- e Evaluation of inclusion and exclusion criteria related to pregnancy testing, urine drug screen, medical history and concomitant medications prior to dosing.
- See Section 7.2.1 for assessments to be performed during a full physical examination.
- g Subjects' alcohol intake will be recorded while on study.

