- Vital signs (blood pressure, pulse rate, respiratory rate, and temperature) should be measured in the supine position after the subject has rested comfortably for approximately 10 minutes. On Day 1, vital signs should be measured within 2 hours predose and 4 hours (± 30 minutes) post-dose. On all other visit days, vital signs are only required to be recorded once during the visit.
- i 12-lead safety ECGs should be measured in the supine position after the subject has rested comfortably for 10 minutes.

cal Study Protocol Amendment 2

[figure not shown]
- WOCBP are required to have pregnancy tests. A blood pregnancy test will be performed at screening and urine pregnancy tests will be performed thereafter. Urine pregnancy test results from local laboratories are acceptable. Negative pregnancy test must be confirmed prior to study drug administration.
- boes not need to be performed if the subject has had a FibroScan in the 6 months prior to screening or liver biopsy in the year prior to screening that confirmed the absence of Metavir F3 fibrosis or F4 cirrhosis.
- See Section 7.1.3 for viral serology parameters.
- m Clinical laboratory and urinalysis parameters are described in Section 7.2.7.
- n Liver function tests only.
- Orugs of abuse included in the screen are described in the inclusion/exclusion criteria. Screening results for drugs of abuse must be reviewed prior to dosing.
- P Study drug will be administered via SC injection as described in Section 6.2.4.
- q Blood samples for PK analysis will be collected at the timepoints listed in Appendix 3.
- As a part of the Week 4 visit, subjects will return to the study center 24-hours after their initial post dose Week 4 PK sample is drawn to have a 24-hour post dose PK sample drawn.
- s Testing should occur again only at Week 36 and Week 48.
- For subjects in Part Two, if HBeAg has become undetectable for 2 consecutive assessments, no further quantitative testing is needed.
- u If a subject experiences ALT flare (as defined by ALT > 2x ULN) additional HBV DNA quantitation sample(s) may be collected
- v CCI
- w CCI
- All AEs related to screening activities must be collected from the time of consent onwards; any other events occurring during the screening period should be reported as medical history. All SAEs must be collected from the time of consent onwards.

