3.3 Hypothesis Testing and Inferential Analyses

Descriptive statistics will be used to summarize all data. No formal hypothesis testing is planned.

3.4 Multiple Comparisons and Multiplicity Adjustments.

Not applicable for this study.

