13.2 Biostatistical methods

All antiviral data collected at scheduled and unscheduled visits will be included in the listings. The results collected as scheduled visits will be included in the summary tables.

The parameter names that will be used in the outputs will comprise the test name and the unit of measure, for example, HBsAg (IU/mL). Parameters will be sorted within parameter class (if present) in alphabetical order within the tables and listings.

Measurements will present summary statistics for the results at the baseline and each scheduled post-baseline visit for each of the parameters. In addition, summaries will be presented for the change from baseline of the antiviral measure to that assessed at baseline values at each scheduled post-baseline visit. See section 3.1 for more detail with regards continuous data representation. Spaghetti plots of \log_{10} -transformed observed values and change from baseline values in HBsAg, HBeAg (Part Two only), CCI [REDACTED] HBV DNA and CCI [REDACTED] will be provided.

Categorical summaries (% of subjects) will present counts and percentages for the reported results at baseline and each post-baseline time point.

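### SAP 3.2 lets anti-HBe already present at screening count towards HBeAg seroconversion, while anti-HBe first positive at Week 16 can count only if a later sample exists

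*SAP*

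**What the plan says.** SAP 3.2 sets two linked rules for Part Two: "HBeAg loss (HBeAg+ subjects only): quantitative HBeAg < 0.14 IU/mL at two or more consecutive measurements" and "HBeAg Seroconversion (HBeAg+ subjects only): HBeAg loss plus anti-HBe positivity at two or more consecutive measurements". Neither refers to baseline.

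The sampling is in the schedule of assessments, Protocol Appendix 2:

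- The row "Blood sample for anti-HBe for Part Two only" is marked at Screening, Week 8, Week 16 (or early termination) and Week 24.
- The row "Blood sample for HBeAg quantitative for Part Two only" is marked at Day 1, Weeks 4, 8, 12 and 16 (or early termination), and Week 24.
- After Week 24, a footnote to both rows says: "Testing should occur again only at Week 36 and Week 48".
- Neither test is marked at Week 20.

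Protocol 4.1 confines scheduled visits after Week 16 to subjects whose HBsAg has fallen by at least 1 log10 from the Day 1 predose level by Week 16.

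Protocol 3.2 lists one combined secondary endpoint for Part Two, HBeAg loss and/or anti-HBe seroconversion at any time, with no confirmation rule. SAP 13.1 repeats the combined count. Protocol 9.7 adds separate summaries of each outcome by cohort and visit. SAP 13.2 states: "Categorical summaries (% of subjects) will present counts and percentages for the reported results at baseline and each post-baseline time point". Part Two is planned as "Up to 15 adult subjects with chronic HBV infection without cirrhosis who are HBeAg-positive on NrtI therapy", and SAP 3.3 states: "No formal hypothesis testing is planned".

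**The concern.** Seroconversion means that antibody appears in someone who did not have it. The rule asks only for two positives in a row. Screening is one of the anti-HBe samples, and Protocol 5.2 requires Part Two subjects to be HBeAg-positive but sets no condition on anti-HBe. Antibody present before the first dose can therefore meet the condition.

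At the other end, HBeAg loss can be confirmed by Week 16 because HBeAg is also drawn at Weeks 4 and 12. Anti-HBe is not drawn at those visits. Whether an antibody first seen at Week 16 can be confirmed depends on further follow-up, and entry to that depends on HBsAg, not on HBeAg response. Two subjects in one cohort with identical HBeAg and anti-HBe results to Week 16 can thus have different chances of being counted.

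At stake is how the seroconversion row reads. It may include subjects who did not convert, and on its own it cannot separate no conversion from no later sample.

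**Working it through.** The plan has no figure of its own to reproduce. The check sets the SAP 3.2 rule against the Appendix 2 schedule.

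**Antibody condition, subjects with no anti-HBe sample after Week 16.** Three samples, each positive or negative, give 2 × 2 × 2 = 8 patterns. Every row assumes that HBeAg loss is confirmed separately.

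| Screening, W8, W16 | Two consecutive positives, as written | Under the fix below |
|---|---|---|
| − − − | no | not counted |
| − − + | no | unconfirmed line |
| − + − | no | not counted |
| − + + | yes | confirmed |
| + − − | no | reported separately |
| + − + | no | reported separately |
| + + − | yes | reported separately |
| + + + | yes | reported separately |

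As written, 3 of 8 patterns qualify, and 2 of those 3 are positive at screening. Requiring post-baseline measurements alone leaves 2 of 8 (− + + and + + +), so that wording does not by itself remove pre-existing antibody. The negative-at-screening condition is needed too.

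**HBeAg condition by Week 16.** Four post-dose samples (Weeks 4, 8, 12 and 16) give 2⁴ = 16 patterns. Those with no two adjacent results below 0.14 IU/mL number 1 (none below) + 4 (one below) + 3 (two, not adjacent) = 8. Confirmed loss therefore arises in 16 − 8 = 8. Combined with anti-HBe pattern − − +, 0 of these 8 are seroconverters under SAP 3.2. All 8 would be if a later anti-HBe sample existed and was positive.

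**Effect of follow-up length.** A first result can be confirmed only if another scheduled sample follows it. Post-dose visits at which this is possible:

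| Last visit attended | Anti-HBe | Quantitative HBeAg |
|---|---|---|
| Week 16 or 20 | 1 of 2 | 3 of 4 |
| Weeks 24–32 | 2 of 3 | 4 of 5 |
| Weeks 36–44 | 3 of 4 | 5 of 6 |
| Week 48 | 4 of 5 | 6 of 7 |

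Exactly one visit, the last, is unconfirmable in every cell. Which visit is last depends on the HBsAg trigger.

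**Combined endpoint.** Seroconversion under SAP 3.2 requires HBeAg loss, so every seroconverter is already counted through HBeAg loss. Neither antibody problem changes the combined count. Only HBeAg loss first seen at the last sample can do so.

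**Weight of one subject.** Part Two has at most 3 cohorts × 5 = 15 subjects, of whom 3 × 4 = 12 receive active drug. One subject is 1/4 = 25.0% of an active cohort, 1/8 = 12.5% of the two planned active cohorts and 1/12 = 8.3% of all three.

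**The case against.** The strongest reply is that the Week 16 miss is simply what any two-measurement rule does at the last visit, and that preferring confirmation to a single positive is a sound, conservative choice. That largely stands. The confirmed definition should be kept. What remains is that the cut-off differs between subjects according to another marker.

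Second, the data are not hidden. SAP 3.1 provides listings sorted by subject and visit that hold all reported and derived data. With at most 15 subjects, a reader can put HBeAg loss and anti-HBe results together by hand. This also stands; only a tabulated count is missing. Table shells for the antiviral outputs are not in the documents, so even that rests on the text of SAP 13 and Protocol 9.7.

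Third, the pattern counts concern the antibody condition alone and carry no frequencies. They also assume the fixed Screening, Week 8 and Week 16 grid, which an early-termination visit or an unscheduled sample would change. That is correct: they show what the rule admits, not how often.

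Fourth, the rule might be read as requiring both markers at the same two measurements. Screening could then not contribute, because Part Two subjects are HBeAg-positive at screening, and + + − would drop out. A subject positive at all three samples would still qualify, so the gap narrows but does not close. The Week 16 result is the same on either reading.

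**Conclusion.** The point holds as a minor defect of definition. As written, SAP 3.2 can count pre-existing anti-HBe as seroconversion, and it cannot count antibody first seen at Week 16 when no later sample, scheduled or unscheduled, exists. Both effects are confined to the separate seroconversion row.

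The documents give no response rates and no frequency of anti-HBe at screening, so the number affected cannot be computed. It may be zero. For the Week 16 miss it cannot exceed the number of Part Two subjects with no later sample, at most 15.

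Three stronger inferences are not supported:

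- A reader might infer that the secondary endpoint undercounts these responders. The combined count includes a subject with confirmed HBeAg loss whatever the anti-HBe result.
- A reader might infer that the SAP contradicts the protocol, which counts events at any time. The protocol gives no confirmation rule, so a stricter SAP definition specifies the endpoint without contradicting it.
- A reader might infer a bias between active drug and placebo. Protocol 1.2.4 reports notable HBsAg reductions on active drug, so active subjects may well enter extended follow-up more often. No rates are given, and no comparison is tested.

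The conclusion assumes that the protocol's anti-HBe seroconversion and the SAP's HBeAg seroconversion are the same outcome. The protocol does not define its term.

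**What to change.** Make two changes before database lock. SAP 16.2 already requires the final SAP to be signed before lock and unblinding.

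1. In SAP 3.2, state that the two consecutive anti-HBe positives must be post-baseline, and count seroconversion among subjects who were anti-HBe negative at screening. Report screening-positive subjects separately.
2. In SAP 13, add a line labelled unconfirmed, with no overlap with the confirmed row, for screening-negative subjects with confirmed HBeAg loss whose first anti-HBe positive is at their last available anti-HBe sample. Add a matching line for HBeAg below 0.14 IU/mL first seen at the last sample.

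Because the unconfirmed antibody line requires the first positive to be at the last sample, a Week 8 positive that reverts at Week 16 does not enter it.

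The cost is a short change to one definition and a few table lines from data already collected, with no new samples and no protocol amendment. The unconfirmed lines are less specific than the confirmed row and must be labelled so. Unequal follow-up itself remains, because it comes from the protocol's HBsAg trigger.
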